There will be no in-person visits for the proposed study. Study interactions will be conducted entirely remotely via JHMI-credentialed Qualtrics surveys, HIPAA-compliant Zoom meetings created by study staff (i.e., using the JHMI HIPAA-compliant instance), or through other approved Johns Hopkins Telemedicine Services (e.g., Polycom). The present study will consist of a *preliminary online screening* (via JHMI-credentialed Qualtrics survey), followed by a more detailed screening televisit for those individuals who meet preliminary screening criteria. Individuals determined to be eligible following the screening televisit will complete three additional televisits: *Treatment*, *Week 7 follow-up*, and *Week 14 follow-up*. Participants will provide contact information for a community observer who will complete two online surveys, one near the *Treatment* visit and one near the *Week 7 follow-up*. Between the treatment visit and the Week 7 follow-up, participants will complete online surveys once per week. In Table 1 below, we provide a summary of the assessments to be administered at each study time point. Detailed measures and descriptions are also appended to the current application in the "Measures" document.

Preliminary Screening. We have created a preliminary screening survey assessing basic demographics and initial eligibility via JHMI-credentialed Qualtrics survey. Links to the survey will be provided via online or paper flyer advertisements (e.g., Psychiatry department website, Google/Facebook ads) or in response to email/telephone inquiry. Individuals who complete the preliminary screening and indicate interest in participation will provide their first name and telephone number as part of the survey. Individuals who meet initial eligibility criteria will be contacted via phone to determine a time for the screening televisit and to receive instructions.

Screening Televisit. Study staff will create a HIPAA-compliant Zoom meeting with the participant, or using other approved Johns Hopkins Telemedicine Services (e.g., Polycom) in the event of technical or other issues with Zoom. The visits will be password-protected and will require the participant to use video

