during the call. Study staff will also use video whenever possible. The study staff will use the Zoom chat function or email to send the participant survey links and will verbally instruct them on how to complete the surveys, beginning with the consent survey. The oral consent form document will be embedded within the Qualtrics survey such that the participant can download the consent form document, or alternatively may be emailed to the participant. The study staff will ask the participant to read aloud the first part of the consent form in order to confirm that they were able to download the document and are able to read English fluently. Then the participant will be provided the opportunity to review the document and ask the study staff any questions they have about participation. This will be followed by a consent quiz administered via Qualtrics survey link. Participants will provide oral consent and answer all of the consent quiz questions correctly prior to proceeding with the remaining screening questionnaires. Following consent, participants will complete standardized medical/substance use history questionnaires as well as surveys to determine their caffeine/cigarette use, caffeine-related problems, and standardized assessments of anxiety, sleep, and gastrointestinal problems as outlined in Table 1. The participant will fill out the surveys via Qualtrics links, or the study staff will interview them and enter their responses on the study staff computers. Study staff will provide instructions to guide them through the assessment completions, review their responses on Qualtrics, and may ask follow-up questions if necessary, to supplement their survey responses. After determining eligibility, participants will be randomized to either the Immediate or Delayed treatment group using an urn randomization procedure accounting for caffeine consumption, age, and sex as was utilized in prior research in our laboratory (Evatt et al., 2016; Sweeney et al., 2019).

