Community Observer. During the screening or treatment visit, participants will be asked to provide the name and contact information (phone number and email address; email will be the preferred method of contact) for a family member, friend, roommate, or significant other for the purposes of online surveys about their caffeine use. The participant will be asked to confirm with their observer that the study team has permission to contact them. The observer will be contacted twice to complete a brief online survey regarding the participants' caffeine use. The first contact will occur soon after the participant has the *Treatment* visit. The second contact will occur near the time of the participant's *Week 7 follow-up* visit.

Treatment Televisit. Participants determined to be eligible following the screening televisit will be scheduled to complete the treatment televisit shortly after screening. For the immediate treatment group, the treatment the *Treatment* visit will generally occur within one week of the screening televisit. The delayed treatment group will have their *Treatment* visit scheduled for a date approximately 7 weeks after screening. During the *Treatment* televisit, study staff will provide the participants with a digital copy of the caffeine reduction treatment manual used in prior studies (Evatt et al., 2016; Sweeney et al., 2019). As in prior research (Sweeney et al., 2019), study staff will give a brief (i.e., generally less than five minutes) description of the manual and instructions on how to gradually reduce their caffeine consumption over a period of six weeks. Participants will also complete assessments to determine their caffeine consumption and cigarette use over the past 7 days as outlined in Table 1. Participants will also be provided with information about their follow-up visits and how to complete weekly surveys.

Weekly Surveys. At seven days following the treatment televisit, participants will receive a request to complete a survey via Qualtrics link sent via email/text. The survey will consist of standard assessments of anxiety, depressed mood, sleep problems, gastrointestinal problems, past week caffeine/cigarette intake, and problems related to caffeine as outlined in Table 1. They will receive a request to complete the same survey once per week (weeks 1-6) until the Week 7 follow-up televisit.

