Week 7 Follow-up Televisit. At approximately 7 weeks after the treatment televisit, participants will complete a follow-up televisit at which they will complete the same measures as previously administered to assess anxiety, depressed mood, sleep problems, gastrointestinal problems, past week caffeine/cigarette use, and caffeine-related problems as outlined in Table 1. Participants will also complete a treatment acceptability survey.

Week 14 Follow-up Televisit. Finally, participants will complete a follow-up visit approximately 14 weeks after the treatment televisit. They will complete all the same assessments as the Week 7 televisit, except they will not repeat the treatment acceptability survey.

Table 1. Study measures according to visit

	Preliminary Online Screening	Screening Televisit	Treatment Televisit	Weekly Surveys (Weeks 1-6)	Week 7 Televisit	Week 14 Televisit
Basic screening questions/demographics ¹	X					
Typical Week Caffeine Survey	X					
AUDIT-C ²	X					
DAST-10 ³	X					
PROMIS-Anxiety-8a ⁴	X			X	X	X
PROMIS-SleepDisturbance-8a ⁴	X			X	X	X
PROMIS-GIDiarrhea-6a ⁴	X			X	X	X
PROMIS-GIReflux-13a1.0 ⁴	X			X	X	X
PROMIS-Depression-8a ⁴	X			X	X	X
Consent Quiz ¹		X				
Medical History Survey ¹		X				
Drug Use History Matrix ¹		X				
Caffeine Timeline Follow-back ¹		X	X		X	X
Past 7 Days Caffeine Survey ¹		X	X	X	X	X
Past 7 Days Cigarette Survey (smokers only) ¹		X	X	X	X	X
Caffeine Problems Survey ¹		X				
Caffeine Use Disorder Questionnaire ¹		X			X	X
Caffeine Use Disorder Interview ¹		X				
GAD-7 ⁵		X			X	X
PSQ-I ⁶		X			X	X
Insomnia Severity Index ⁷		X			X	X
GSRS ⁸		X			X	X
Treatment Acceptability Survey/Interview ¹					X	
Observer Rating Survey (Completed by Community Observer) ¹				X		X

Note. Detailed descriptions of all measures are appended to the present IRB application in the "Measures" document. ¹Study team-generated measure/survey based on prior research (e.g., Sweeney et al. 2019, 2020). ²Alcohol Use Disorders Identification Test-C, Bush et al., 1998. ³Drug Abuse Screening Test, Skinner 1982. ⁴Patient-Reported Outcomes Measurement Information System, Cella et al., 2010, Rothrock et al., 2010. ⁵Generalized Anxiety Disorder-7, Spitzer et al., 2006. ⁶Pittsburgh Sleep Quality Index, Buysse et al., 1989. ⁷Bastien et al., 2001. ⁸Gastrointestinal Symptom Rating Scale, Svedlund et al., 1988.

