b. If your study involves data/biospecimens from participants enrolled under other research studies with a written consent or under a waiver of consent, please list the IRB application numbers for those studies. Please note: Certificate of Confidentiality (CoC) protections applied to the data in source studies funded by NIH or CDC will extend to this new study if the funding was active in 2016. If this situation applies, Section 36, question 4 in the application will need to be answered "Yes" and "Hopkins Faculty" should be selected in question 7. No other documents are required.

This study does not involve data or biospecimens from participants enrolled in other research studies.

c. Study duration and number of study visits required of research participants.

Participants will be asked to complete online preliminary screening via Qualtrics survey, four televisits (screening, treatment, 7 week follow-up, 14 week follow-up), and complete six surveys over six weeks

(weeks 1-6 following treatment televisit), as described in detail above in study procedures and in Table 1. The screening televisit is anticipated to take less than 1.5 hours. All other televisits are expected to take less than 30 minutes. The six weekly surveys (weeks 1-6 following treatment televisit) are anticipated to take approximately 5-10 minutes once per week. The anticipated study duration is approximately 15 weeks from the time of the screening televisit to the final televisit at 14-weeks for those in the immediate intervention group. For those in the delayed intervention group, the anticipated study duration is approximately 21 weeks due to the programmed delay between the screening televisit and the treatment televisit. The duration of participation will be in part dependent on participant and study staff scheduling and availability. There is no evidence to suggest that the difference in timing of visits and measures will adversely affect the participants or the validity of the study. On those occasions on which the timing of meetings, sessions or measures deviate substantially from the time frames in the protocol, we will report these as deviations in the Continuing Review.

- d. Blinding, including justification for blinding or not blinding the trial, if applicable.

There is no blinding component to the proposed research.

- e. Justification of why participants will not receive routine care or will have current therapy stopped.

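### State one answer mode for the symptom scales and collect the Week 7 acceptability ratings by private link: the protocol allows staff interview at Screening and leaves the follow-up mode open

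*Combined protocol and SAP*

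**What the plan says.** **Screening (section 4.a, Screening Televisit).** Participants fill out the surveys by Qualtrics link, "or the study staff will interview them and enter their responses on the study staff computers". Staff also "review their responses on Qualtrics, and may ask follow-up questions if necessary, to supplement their survey responses". The call is live: "The visits will be password-protected and will require the participant to use video". Allocation follows: "After determining eligibility, participants will be randomized to either the Immediate or Delayed treatment group".

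**Treatment and weekly surveys (section 4.a).** At the Treatment televisit, "study staff will provide the participants with a digital copy of the caffeine reduction treatment manual". In weeks 1 to 6, "participants will receive a request to complete a survey via Qualtrics link sent via email/text".

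**Follow-up (section 4.a, Week 7 and Week 14).** The measures already given are repeated on a televisit. The text does not say whether participants answer them alone or are asked by staff. A treatment acceptability survey is added at Week 7 only. Table 1 lists it as "Treatment Acceptability Survey/Interview".

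**Blinding (section 4.d).** "There is no blinding component to the proposed research".

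**Analysis (section 7).** Section 7.a makes the primary outcome two things: completion, and self-reported agreement with the acceptability items. Section 7.c summarises agreement as mean and standard deviation on a visual analog scale. For the secondary outcomes, 7.c gives means and standard deviations at the screening, treatment, Week 7 and Week 14 visits, and pre/post effect sizes.

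**The concern.** Rating scales can be answered differently when a person reads and asks the items than when the respondent completes them alone. If mode is not fixed, part of a before-after change in a symptom score can reflect how the question was put.

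The acceptability ratings are the more exposed outcome. Items such as whether the guide was helpful, or whether it was read, are answered on a call with the study team that supplied the guide. There is no comparison group for these ratings, so any tendency to give agreeable answers goes straight into the reported mean. That mean is part of the evidence on which a later trial of the remote intervention would be justified.

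**Working it through.** No arithmetic applies: the plan gives no figure for mode or interviewer effects, so there is nothing to reproduce. The check sets Table 1 against the visit descriptions in section 4.a, measure by measure.

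1. **GAD-7, Pittsburgh sleep index, Insomnia Severity Index, GSRS.** Given at Screening, Week 7 and Week 14, all televisits. At Screening two modes are allowed. At Weeks 7 and 14 none is stated. A change of mode is possible, but none is documented.

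2. **PROMIS anxiety, sleep disturbance, diarrhea, reflux and depression.** First given in the preliminary online screening, then in the weekly link surveys, then at the Week 7 and Week 14 televisits. The setting changes from an online form to a staffed call between baseline and follow-up, even if nobody is interviewed. This follows from Table 1 without inference.

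3. **Past 7 Days Caffeine Survey and Caffeine Timeline Follow-back.** The first is taken at televisits and in the weekly link surveys; the second at televisits only. Section 7.c does not list the weekly surveys among the time points it summarises, so their self-completed mode is not shown to enter the pre/post effect sizes.

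4. **Acceptability.** Given once, at Week 7. Its mode can vary between participants but not between visits. The Week 7 text, 7.a and 7.c call it a survey, and 7.c scores it on a visual analog scale, a format that suits self-completion. Only the Table 1 label mentions an interview. The label and the text need reconciling.

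5. **Who collects.** Section 4.a has study staff both provide the manual and run the televisits. Section 4.d rules out blinding. No separate assessor is named.

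6. **What is protected.** Completion does not depend on how answers are entered. Community observers rate the participant's caffeine use in two online surveys. That gives partial support for intake and none for symptoms or acceptability.

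Steps 1, 2 and 4 show that mode is open for the symptom scales and ambiguous for acceptability. Step 5 shows nothing in the design that separates the acceptability ratings from the people who gave the manual.

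**The case against.** The strongest reply is that the interview option sits in the Screening paragraph alone. Screening precedes randomization and the manual, so there is no group to know and no deliverer to please. Staff review of answers also serves eligibility there. This stands. A reader might infer that unblinded staff interview participants at Weeks 7 and 14, or that mode is picked visit by visit. The documents say neither. They are silent on follow-up mode, and only the Table 1 label hints at an interview.

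A reader might also infer that every before-after effect size is distorted. That is too broad, for the reasons in steps 1 and 3 of the check.

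A third tempting inference is that staff entry widens differential reporting between the immediate and delayed groups under secondary objective (c). Unblinded self-report carries that risk in any mode, and nothing in the documents shows that interviewing enlarges it.

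Other points on this side have weight. The acceptability text points mostly to self-completion. The pilot is descriptive and sets no acceptability threshold. The staff contact that delivers the manual is brief. The appended Measures document, which was not available for this review, may state modes.

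These points narrow the concern without removing it. Two modes are expressly allowed for baseline scales, the PROMIS change of setting is in Table 1, and acceptability is still answered on a staffed call with the delivering team.

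**Conclusion.** The point holds as a cheap improvement to the design. Mode of answering is not fixed for the standardized symptom scales, so it may differ between participants or between baseline and follow-up. The acceptability ratings are collected once, without a comparator, on a live call run by unblinded study staff, under a table label that disagrees with the text. Answers may lean favourable; the documents do not show that they do.

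No size can be put on this from the documents, and none is offered. The effect is confined to acceptability, which is half of the primary outcome, and to the self-reported secondary measures. Completion is untouched, and observer ratings partly corroborate caffeine use.

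The conclusion assumes that the Measures document does not already fix the mode. If it does, the rule should be brought into section 4.a, and the Table 1 label would still need aligning.

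**What to change.** - In section 4.a, state that the standardized symptom scales and the acceptability items are self-completed on the Qualtrics link at every visit where they are given and in both groups, with staff giving technical help only. Record the mode for any exception.
- Collect the visual analog acceptability items by private link, before any debrief interview. Set survey access so that staff on the call do not see individual answers, and tell participants so. The access setting has to come first, because the Screening text has staff reviewing responses.
- Align the Table 1 label with the text. If a separate interview is intended, list it as its own row.
- Staff review of Screening answers for eligibility can stay, as can the Caffeine Use Disorder Interview and a scripted Timeline Follow-back.

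**Cost:** protocol wording and a survey-access restriction. Fewer items can be clarified live. Participants must already read English fluently and have a video-capable device (section 5), so self-completion should add little burden.

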There will be no anticipated disruption to any ongoing treatment or routine care.

- f. Justification for inclusion of a placebo or non-treatment group.

There will be no anticipated placebo or non-treatment group. These are pilot or preliminary data that may support a future randomized trial which would have a separate IRB approval.

- g. Definition of treatment failure or participant removal criteria.

Participants who are not eligible or who are noncompliant with study tasks will be removed from the study early. There are no other early stopping rules in the study.

- h. Description of what happens to participants receiving therapy when study ends or if a participant's participation in the study ends prematurely.

The intervention consists solely of the treatment manual and brief instructions provided at the treatment televisit, and is not accompanied by any ongoing therapy (Sweeney et al., 2019). All participants who complete the treatment televisit will be able to keep their copy of the treatment manual.

5. Inclusion/Exclusion Criteria

Inclusion Criteria

1. Between 18-75 years old
2. Reside in the United States
3. Read, write, and speak English fluently
4. Able to access a video camera on a smartphone, tablet, or other computer
5. Able to receive text messages or emails (or both)
6. Consume greater than or equal to 200 mg caffeine per day in a typical week
7. Indicate a problem that is caused or worsened by caffeine from among the following options: sleep problems, anxiety or nervousness, frequent urination, heartburn or other digestive issues, feel dependent on or addicted to caffeine

8. Interested in getting help to gradually reduce or eliminate caffeine consumption as part of a research study

Exclusion Criteria

1. Evidence of significant depressive symptoms assessed via PROMIS-Depression-8a and medical history
2. Evidence of problematic alcohol use assessed via the AUDIT-C and medical/substance use history
3. Evidence of problematic substance use other than alcohol, nicotine, or caffeine assessed via the DAST-10 and medical/substance use history
4. Evidence of a significant psychiatric disorder, presentation of acute psychiatric symptoms, or any other mental illness that, in the opinion of the investigators, may complicate participation in the study. [Anxiety and sleep disorders are not anticipated to interfere with study participation and will not generally be exclusionary]

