Protection against risks of the study procedures: All participants in this study will be thoroughly informed of the potential risks, including of caffeine withdrawal, during the oral informed consent process. Because participation is voluntary, participants can withdraw at any time if they find the behavioral procedures or caffeine withdrawal effects undesirable. The gradual reduction over a period of weeks was specifically designed to reduce the frequency and severity of caffeine withdrawal. The study team carefully reviews medical and social history information from Screening to determine eligibility, and a member of the Behavioral Pharmacology Research Unit (BPRU) medical staff will be consulted if there are medical concerns judged to potentially impact participation.

Protection against risk of a breach in confidentiality: Research staff are highly trained to maintain participant confidentiality. Records and data are maintained on encrypted staff computers and HIPAA-compliant JHMI-credentialed Qualtrics surveys and will only be released outside of the study team with written authorization. Study IDs are used on data collection instruments and in electronic data storage wherever possible in place of any personally identifying information. The identity of subjects is not revealed in written records and documents with subjects' names are shredded before disposal. Televisits will only be arranged via password-protected Zoom meetings with study staff created in the JHMI HIPAA-compliant instance, or through other approved Johns Hopkins Telemedicine Services (e.g., Polycom) in the event of technical or other issues with Zoom. No recordings will be made of participant interactions. Regarding the observer ratings, participants are informed when they identify a community observer of the questions the observer will answer, and that none of the participant's other study information will be shared with the observer and that the observer ratings will not be shared with the participant. Staff have clear instructions to limit the information shared between participant and observer to only that described in the consent form and specified study measures.

c. Plan for reporting unanticipated problems or study deviations.

All unanticipated problems and adverse events will be reported to the IRB and other relevant agencies as required and described in the Data and Safety Monitoring Plan.

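### The delayed arm starts caffeine reduction about 7 weeks after its last exclusion-related check, with no depression or health-change measure at the Treatment televisit

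*Combined protocol and SAP*

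**What the plan says.** **When eligibility is settled.** Section 4.a (Screening Televisit) states: "After determining eligibility, participants will be randomized to either the Immediate or Delayed treatment group using an urn randomization procedure". Section 8.b agrees: "The study team carefully reviews medical and social history information from Screening to determine eligibility".

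**What is excluded.** Section 5 lists "Evidence of significant depressive symptoms assessed via PROMIS-Depression-8a and medical history" and "Evidence of problematic alcohol use assessed via the AUDIT-C and medical/substance use history". Other problematic substance use is judged from the DAST-10 and history. Psychiatric and medical conditions are left to the investigators' opinion.

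**When the manual is given.** For the immediate arm the Treatment "visit will generally occur within one week of the screening televisit". The delayed arm has its Treatment "visit scheduled for a date approximately 7 weeks after screening".

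**What is measured at that visit.** Section 4.a (Treatment Televisit) says: "Participants will also complete assessments to determine their caffeine consumption and cigarette use over the past 7 days as outlined in Table 1". The Treatment column of Table 1 matches: Caffeine Timeline Follow-back, Past 7 Days Caffeine Survey and, for smokers, Past 7 Days Cigarette Survey.

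**Related text.**
- Section 4.g provides for early removal of ineligible participants but names no time point or assessment.
- Section 7.c plans means and standard deviations of Table 1's standardised assessments at screening, treatment, Week 7 and Week 14.
- Section 8.a lists depressed mood among the withdrawal symptoms. It also calls the procedures benign and treats withdrawal as short-lived and of low medical risk.

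**The concern.** The information behind the exclusions is about 6 weeks older in the delayed arm than in the immediate arm when reduction starts. No study visit or survey is scheduled for the delayed arm in between, because the weekly surveys begin only after the Treatment televisit.

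Two things are at stake:

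- **Safety information.** A participant whose mood, substance use or health changes during the wait begins reduction with no scheduled measure that would show it.
- **Interpretation.** Depressed mood is both an exclusion topic and a listed withdrawal effect. Without a score taken just before the manual is given, low mood in the first weekly survey cannot be assigned to the waiting period or to the reduction.

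**Working it through.** **1. The plan's own durations.** Section 4.c gives about 15 weeks (immediate) and 21 weeks (delayed) from the Screening televisit to the last visit. With final follow-up 14 weeks after Treatment:

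- Immediate: 1 + 14 = 15 weeks.
- Delayed: 7 + 14 = 21 weeks.

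Both figures reproduce. The difference in time from Screening to manual is 7 − 1 = about 6 weeks.

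**2. Which exclusion measures are repeated (Table 1).**

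| Measure | Before the manual | At Treatment | Later |
|---|---|---|---|
| PROMIS-Depression-8a | Preliminary survey | No | Weeks 1–6, Week 7, Week 14 |
| AUDIT-C | Preliminary survey | No | No |
| DAST-10 | Preliminary survey | No | No |
| Medical History Survey | Screening televisit | No | No |
| Drug Use History Matrix | Screening televisit | No | No |

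None of the five is taken at Treatment, and one of the five is taken at any later point.

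**3. The blind interval for depression.** The first score after the manual comes 7 days after Treatment. Counted from the Screening televisit:

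- Immediate: about 1 + 1 = 2 weeks, of which about 1 precedes reduction.
- Delayed: about 7 + 1 = 8 weeks, of which about 7 precede reduction.

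The previous depression score is from the preliminary survey. Both intervals are therefore longer by an amount the protocol does not state.

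**4. How many people.** The planned total is 100 (section 7.c); its power justification has no bearing here. The allocation ratio is not stated. Assuming equal arms, 100 / 2 = 50 people are exposed to the gap. The documents give no rate of newly meeting an exclusion over 7 weeks, so the rates p below are assumptions. Expected number = 50 × p; chance of at least one = 1 − (1 − p)^50.

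| Assumed p | Expected number | Chance of at least one |
|---|---|---|
| 1% | 0.5 | 40% |
| 2% | 1 | 64% |
| 5% | 2.5 | 92% |
| 10% | 5 | 99% |

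If the delayed arm held 40 to 60 people, the expected number would run from 40 × 1% = 0.4 to 60 × 10% = 6.

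**5. Section 7.c against Table 1.** Section 7.c expects standardised assessments at the treatment visit. Of the Table 1 measures scheduled there, all are study-generated caffeine or cigarette instruments. PROMIS-Depression-8a is a standardised assessment that section 7.c would summarise at Treatment but that Table 1 does not collect.

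**The case against.** The strongest reply is that no eligibility rule is broken. Sections 4.a and 8.b consistently place the eligibility decision at screening, before randomisation, and nothing requires the criteria to hold again when the manual is given. That stands. Checking only at entry is a defensible choice if the protocol says so.

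The protocol also describes low stakes: a gradual taper, freedom to withdraw, and medical-staff consultation where concerns arise. The Treatment televisit is a live video call, so staff might notice acute symptoms. Section 8.c refers to a Data and Safety Monitoring Plan that is not among the documents, so further safeguards cannot be ruled out. These points limit the weight of the concern.

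Three stronger readings are tempting, and the documents do not support them:

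- **That half the sample would start reduction while meeting an exclusion.** About half is the number exposed to the gap, and only under equal allocation. The number affected is unknown.
- **That new problems would go wholly unseen.** PROMIS-Depression-8a returns 7 days after the manual and weekly after that. For depression the gap is the missing score before reduction, together with the absence of any stated response to later scores. Only the alcohol, drug and medical exclusions lack any later measure.
- **That the checks are up to date in the immediate arm.** Three of the questionnaires come from the preliminary survey, at an unstated interval before the Screening televisit, so this is not shown for either arm.

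A re-check also carries a risk of its own. Read with the removal sentence in section 4.g, it could lead to removal after randomisation mainly in the delayed arm. The fix has to deal with that.

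**Conclusion.** The point holds as a modest gap in measurement and clarity. It is not a breach of the protocol's eligibility rules. The delayed arm begins reduction about 7 weeks after the Screening televisit, against generally one week or less in the immediate arm, and neither arm has a depression or health-change measure at the Treatment televisit. Depressive symptoms arising during the wait cannot be distinguished from those following reduction, and alcohol, drug and medical changes have no later scheduled measure.

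The timing and the schedule come directly from the protocol. The figure of about 50 exposed rests on assumed equal arms, and every figure for people affected rests on an assumed rate. The protocol's own account puts the risk as low. The case for a change is that it costs little and also supplies a treatment-visit score that section 7.c already promises.

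**What to change.** 1. **Section 4.a and Table 1:** add PROMIS-Depression-8a and one question on health or substance-use changes since screening at the Treatment televisit, in both arms, before the manual is given. This also reconciles Table 1 with section 7.c for this one measure; the other standardised assessments remain to be reconciled.
2. **Sections 4.a, 4.g, 5 and 8.b:** reconcile the text so that it says whether the exclusions apply at randomisation only or also when the manual is given. That choice, and any clinical action on the answers, belongs to the investigators.
3. **Section 4.g:** amend the removal sentence so that a change found after randomisation does not take the participant out of follow-up or out of the randomised comparison.

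The cost is nine items (8 + 1) at an existing visit expected to last under 30 minutes, plus a protocol amendment. No new visits or staff are needed. The downside is a few minutes per participant and an occasional medical consultation.
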